30-day hospitalization	Admission date to a Partners hospital within 30 calendar days of incident PCI.
90-day hospitalization	Admission date to a Partners hospital within 90 calendar days of incident PCI.
Cardiac reason for hospitalization	Admission for chief complaint of cardiac etiology (ie CAD, CHF, arrhythmia), admission requiring cardiac consultation or admission to a cardiology ward unit.
30-day ER visit	Presentation to Partners ER or Urgent Care within 30 calendar days of incident PCI without subsequent hospitalization.
90-day ER visit	Presentation to Partners ER or Urgent Care within 90 calendar days of incident PCI without subsequent hospitalization.

90-day Cardiac Rehabilitation	Attendance of cardiac rehabilitation intake session at a Partners facility within 90 calendar days of incident PCI.
30-day Cardiac Follow Up	Attendance of cardiac outpatient follow up appointment at a Partners facility (with MD or NP) within 30 calendar days of incident PCI
30-day repeat PCI	Repeat percutaneous intervention on same or new coronary lesion within 30 days of incident PCI.
90-day repeat PCI	Repeat percutaneous intervention on same or new coronary lesion within 90 days of incident PCI.
90-day Stroke	Chart diagnosis of or admission for new stroke within 90 calendar days of incident PCI as noted in Partners EHR.
90-day Nonfatal MI	Chart diagnosis of or admission for myocardial infarction (without subsequent death) within 90 calendar days of incident PCI as noted in Partners EHR.
90-day CV Death	Documentation of death within 90 calendar days of incident PCI noted in Partners EHR with cause specified as secondary to CAD, CHF, Arrhythmia or other clear cardiovascular reason.
90-day All Cause Death	Documentation of death within 90 calendar days of incident PCI noted in Partners EHR.
Conversion Rate	Number of patients enrolled in Wellframe out of number of total patients eligible for study.
Days Enrolled	Number of days between patient onboarded with Wellframe app and marked done by clinical staff.
Medication Reminders	Number of medication reminders set up by patient (0 if patient has not set up any reminders).
30-day Medication Adherence	Percentage of medication reminder tasks completed within 30 days on app. (Null if no patient reminders set up)
90-day Medication Adherence	Percentage of medication reminder tasks completed within 90 days on app. (Null if no patient reminders set up)

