Primary analysis will verify balance in matching (unadjusted) via Chi-squared model for binary variables and ANOVA for categorical variables

I. Engagement Analyses: Overall engagement by patients in the intervention arm with the Wellframe application will be assessed by evaluating the number of days or weeks with at least one task completed (including surveys done, content read, activity goals reached and medication reminders used) within both a 30- and 90-day period. Individual task completion rates will also be assessed and reported within 30- and 90-day periods. Use of messaging between patients and health advocates will also be assessed during a 30- and 90-day period. Changes in these metrics across 30- to 90-days will be evaluated.

J. Exploratory Analyses:

We will compare subgroups (MI/elective) using linear regression across the 30-day engagement metrics above to evaluate predictors of engagement (adjusting for both 30-day engagement as well as matching covariates such as age, sex, PCI type, state, insurance, partners PCP and site).

We will use the Cox Proportional Hazards model to assess efficacy of the intervention on lowering rate of ER visits for cardiovascular reasons, ER visits for all causes and hospitalizations for all reasons.

We will use the Cox Proportional Hazards model to assess efficacy of the intervention on reducing rates of repeat PCI, stroke, non-fatal MI, cardiovascular cause of death and all cause death within 90 days of enrollment.

We will use the Cox Proportional Hazards model to assess for improvement in percentage of patients adhering to cardiovascular follow up appointments within 30 days of discharge.

K. Type I Error Control: We will control for error by limiting our primary outcome to 90-day cardiac rehabilitation enrollment. All subsequent analysis, including secondary outcomes, will be considered exploratory.

L. References:

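### Repeat PCI and hospitalization in SAP D.7 make no exception for procedures already planned at the index PCI, so exploratory comparisons in Section J may be diluted or biased

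*SAP*

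**What the plan says.** SAP D.7 defines repeat PCI in two windows: "Repeat percutaneous intervention on same or new coronary lesion within 30 days of incident PCI" and "Repeat percutaneous intervention on same or new coronary lesion within 90 days of incident PCI". Hospitalization is likewise defined by date alone: "Admission date to a Partners hospital within 30 calendar days of incident PCI" and "Admission date to a Partners hospital within 90 calendar days of incident PCI". An admission counts as cardiac if the chief complaint is cardiac (coronary disease is among the examples), or if it is an "admission requiring cardiac consultation or admission to a cardiology ward unit".

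SAP Section J uses Cox models to "assess efficacy of the intervention on reducing rates of repeat PCI, stroke, non-fatal MI, cardiovascular cause of death and all cause death", all within 90 days. It also uses them for lowering "ER visits for all causes and hospitalizations for all reasons". The table shells list 30- and 90-day readmission, all-cause and cardiovascular, and a MACE row whose components are not given.

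SAP C.1 and K make 90-day cardiac rehabilitation enrollment the only primary outcome and treat the rest as exploratory. Neither document mentions planned or staged procedures. The control matching in D.2.b covers MI/elective status and site, but not whether a further procedure was planned.

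**The concern.** A second PCI arranged at the time of the index PCI meets the repeat-PCI definition, because a new lesion qualifies. If it involves a Partners admission, it is also an all-cause hospitalization. It will usually be a cardiac one too, since a coronary chief complaint or a cardiology ward stay suffices. One scheduled procedure can therefore count against the app on three outcomes.

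The intervention is education, reminders, messaging and non-clinical coaching. Nothing in the documents suggests that it should stop a procedure already scheduled. Such events add noise if they are equally common in both groups. If they are not, they add bias. Equality cannot be assumed: controls had their PCI from 2015 to 2017, participants were enrolled from February 2018 to June 2019, and matching does not cover planned staging.

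**Working it through.** **Inputs.** The protocol's Power Analysis gives 150 participants, 600 controls, alpha 0.05, a 2.5-fold effect, 5% readmission and at least 80% power. It does not say which group has the 5%, or the direction. SAP D.8 uses 450 controls, for a different outcome. The planned-admission rate *s* is an assumption, with a range of 0 to 10%.

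**Formula.** Two-sided comparison of two proportions, pooled variance under the null:

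power = Φ[(|p1 − p2| − 1.96·s0)/s1], with s0 = √(p̄(1 − p̄)(1/n1 + 1/n2)) and s1 = √(p1(1 − p1)/n1 + p2(1 − p2)/n2).

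Section J plans Cox models, so these power figures are approximate.

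**Step 1: the protocol's own figure.** Take app 5%, control 12.5%, 150 v 600.
- p̄ = (7.5 + 75)/750 = 0.11; s0 = 0.02856; s1 = 0.02234.
- z = (0.075 − 0.05598)/0.02234 = 0.851, so power is 80.3%.

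This matches the stated figure closely. With control 5% and app 2%, power is only 32%. With control 5% and app 12.5% it is 86%, but that is an increase in readmission.

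**Step 2: equal planned rates in both groups.** Assume planned admissions are independent of unplanned ones: p′ = 1 − (1 − p)(1 − s). At s = 5%, control = 1 − 0.875 × 0.95 = 16.9% and app = 1 − 0.95 × 0.95 = 9.75%.

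| s | Control | App | Ratio | Power, 600 controls | Power, 450 controls |
|---|---|---|---|---|---|
| 0 | 12.5% | 5.0% | 0.40 | 80% | 78% |
| 1% | 13.4% | 5.95% | 0.44 | 75% | 73% |
| 5% | 16.9% | 9.75% | 0.58 | 59% | 57% |
| 10% | 21.3% | 14.5% | 0.68 | 45% | 43% |

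The risk difference changes little (7.5 points at s = 0, 0.2125 − 0.145 = 6.75 points at s = 10%). What moves is the ratio, and power falls mainly because the variance grows.

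**Step 3: a less favourable reading for the point.** Suppose the 5% is already total control readmission, that the app cuts only the unplanned part 2.5-fold, and that there are 450 controls.
- 1% planned: all-event 5% v 1% + 4%/2.5 = 2.6%, ratio 0.52, power 20.1%. Unplanned only: 4% v 1.6%, ratio 0.40, power 24.6%.
- 2% planned: all-event 5% v 2% + 3%/2.5 = 3.2%, ratio 0.64, power 12.3%. Unplanned only: 3% v 1.2%, ratio 0.40, power 17.7%.

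Excluding planned events gains about 5 points, because it also removes events.

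**Step 4: unequal planned rates, no app effect.** Take 5% unplanned readmission in both groups, 150 v 450.
- Planned 5% in controls, 2% in app users: (1 − 0.95 × 0.98)/(1 − 0.95 × 0.95) = 6.9%/9.75%, ratio 0.71, an apparent benefit. The chance of a significant result is about 16%.
- The reverse: 9.75%/6.9%, ratio 1.41, an apparent harm. The chance of a significant result is about 22%.

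**The case against.** Much of the case on the other side stands.

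- **Status.** These outcomes are exploratory in the SAP. A reader might infer that the trial's primary result is compromised, because the protocol's outcome list and power section label 30-day readmission as primary. The documents do not support that: the protocol's Aim 3 names rehabilitation enrollment as primary, and the later SAP makes it the only one. The protocol's inconsistency is a separate matter and adds no weight here.
- **Reach.** The 30-day repeat-PCI variable is defined but not tested in Section J, and repeat PCI has no table shell of its own. MACE may or may not include it.
- **Size.** The planned rate is wholly assumed. A staged procedure done during the index stay adds no readmission, and one done without admission affects only repeat PCI.
- **Legitimacy and cost.** All-cause admission is a defensible endpoint that needs no judgement. Planned intent must come from the index record, which D.7 does not otherwise require for this purpose, and the protocol only permits chart review of controls. The study is open-label. The SAP is dated December 2019, after follow-up ended in September 2019, so the change would come after data collection.

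These points limit the importance but do not remove the point. Counting planned events equally in both groups still weakens the ratio, and equality between the two eras is not secured by the matching.

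**Conclusion.** The definitions as written count scheduled procedures as events that the app is meant to reduce. This is a minor weakness in exploratory outcomes; 90-day rehabilitation enrollment and its power statement are untouched.

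The size rests on assumption. With 1% to 10% planned admissions added equally to both groups, the ratio moves from 0.40 to 0.44-0.68 and power from 80% to 75%-45%. If the protocol's 5% is instead total control readmission, excluding 1% to 2% planned admissions gains about 5 points of power from a low base. With unequal planned rates of 5% and 2%, a true ratio of 1 appears as 0.71 or 1.41, depending on which group has more.

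Two stronger readings go too far. One is that the app cannot change these outcomes: only the planned events are beyond its reach, and the remaining admissions and repeat PCIs may respond. The other is that the effect must be dilution: that holds only if planned rates are similar in the two groups, and the documents do not show whether they are.

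**What to change.** In D.7, add unplanned versions of repeat PCI and hospitalization at 30 and 90 days. Exclude only events documented as planned in the index procedure or discharge record. Apply the same written rule to participants and controls and, where possible, have the record read without knowledge of group. Use these versions in Section J and in the readmission tables, and in MACE if repeat PCI is a component. Report the all-event versions as supportive rows, and state that the change was made after follow-up had ended. Readers can then see whether planned procedures drive any difference.

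The cost is one flag from the index record for each participant or control with an event, some reviewer judgement in an open-label study, and fewer counted events.

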The Health Advocate builds a supportive, coaching relationship with the patient and provides non-clinical support, encouragement, and accountability to maximize engagement. The Health Advocate sends encouraging messages and addresses patients’ non-clinical needs, facilitates patient adherence to care programs, promotes patient program retention and engagement through multiple communication channels, and monitors the patients’ Mobile App behaviors. As a part of these activities, the Health

Advocate directly encourages patients to complete the tasks in their Wellframe care program, including reading their health education and completing their surveys.

The Health Advocate co-manages patients with the clinical team via the Wellframe dashboard. The Health Advocate facilitates triage of clinical needs to clinical staff. As a non-clinician, the Health Advocate operates under the supervision of Wellframe's team of licensed clinicians (physicians and nurse practitioners), and all patient communication adheres to structured protocols and guidelines set forth by Wellframe clinical leadership.

III. RESEARCH DESIGN AND METHODS

Sample size: 150 post-PCI at Massachusetts General Hospital (MGH) and Brigham & Women's Hospital (BWH): 100 with myocardial infarction, 50 with symptomatic coronary artery disease without myocardial infarction

Inclusion/Exclusion Criteria

- Acute myocardial infarction – defined by typical symptoms, characteristic kinetics of cardiac biomarkers or characteristic EKG changes

Or

Symptomatic coronary artery disease without myocardial infarction – defined by typical symptoms (i.e. angina) and signs (i.e. abnormal non-invasive cardiovascular testing: stress testing or coronary CTA)

Inclusion Criteria

- Age 21-85
- English-speaking
- PCI: balloon angioplasty, bare-metal stent, or drug-eluting stent at MGH
- Smartphone or Tablet (iOS or Android)
- Long term provider in Massachusetts (or records available through Care Everywhere)

Exclusion Criteria

- Recent (within 1mo) illicit substance use or alcohol abuse
- In-hospital AMI
- Known pregnancy
- Dementia or cognitive disability
- Incarceration

Study Outcomes

Clinical and Utilization Outcomes

Clinical outcomes will be ascertained from electronic medical records. Patients will also be called at 90 days to determine potential readmission, representation, and cardiac rehabilitation enrollment at other hospitals or clinics during the follow-up period. The following outcomes will be assessed:

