A Smartphone-based Application Post-myocardial Infarction to Manage Cardiovascular Disease Risk
NCT03416920
Version Date: 12/28/19
[name], [name]
Statistical Analysis Plan

A. Background and Rationale:

The period between inpatient hospitalization for symptomatic coronary artery disease (CAD) and post-discharge office consultation remains a vulnerable interval for adverse outcomes. We sought to develop and evaluate a tool to help guide, reassure and educate patients during this susceptible time.

We aimed to recruit and onboard 150 patients who have undergone percutaneous coronary intervention (PCI) with a novel mobile health platform developed specifically for this population. The mobile application (app) includes educational about specific procedures (PCI) and diagnoses (coronary artery disease, acute myocardial infarction) as well as lifestyle education programs (hypertension, hyperlipidemia, diabetes, weight loss, smoking cessation). The app also utilizes live health care coaches to interact with participants virtually to facilitate adherence to outpatient follow up, enrollment in cardiac rehabilitation and achieve individually targeted goals.

B. Hypothesis:

Our overall hypothesis is that engagement with our smartphone application post PCI will correlate with increased rates of enrollment in cardiac rehabilitation amongst study participants as compared to historical controls.

C. Endpoints:

- C.1. Primary:** 90-day cardiac rehabilitation enrollment rates
- C.2. Secondary:** 30-day cardiac outpatient follow up attendance

D. General Study Design and Plan

- D.1. Design:** Multi-site stratified single-arm prospective study

- D.2. Type of controls:** Historical

D.2.a. Control ascertainment: Query of Research Patient Data Registry (RPDR) database (a centralized clinical data registry that gathers clinical information from various Partners hospital systems with a query tool that provides users with detailed medical record information on identified patient populations that meet user-defined characteristics and criteria such as diagnoses, procedures, medications and/or laboratory results) for subjects aged 21-85 years old who underwent percutaneous coronary intervention from 01/01/2015 through 12/31/2017.

D.2.b. Control matching: Controls matched for Age, Sex (M/F), State (MA/non-MA), PCI Type (MI/Elective), DM2 (Y/N), Partners PCP (Y/N), Insurance Type (Commercial/Medicaid/Medicare/Other), Site (MGH/BWH)

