- D.3. Level and method of blinding:** Open-label

- D.4. Randomization time point:** NA

- D.5. Timeframe of all study periods:**

D.5.a. Intervention arm: screening (02/2018-06/2019), baseline (02/2018-06/2019), intervention period (02/2018-09/2019), follow-up (05/2019-09/2019)

D.5.b. Historical control arm: baseline (01/2015-12/2017), follow-up (03/2015-03/2018)

D.6. Inclusion/Exclusion criteria:

D.6.a: Inclusion: 21-85 years old, fluency in English language, underwent PCI at either MGH or BWH during screening period for either symptomatic CAD or ACS, own a smartphone or tablet

D.6.b: Exclusion: Recent (<1mo) drug or alcohol abuse, in hospital AMI, pregnancy, cognitive delay/dementia, incarceration

D.7. Study variables:

Age	Age at time of enrollment into study as coded into Partners EHR
Sex	Gender as coded into Partners EHR
State	State of residence (Massachusetts vs Non-Massachusetts) at time of enrollment into study as coded into Partners EHR
PCI Type	Reason for percutaneous coronary intervention (PCI). Myocardial infarction (MI) coded as chart diagnosis of MI or positive serologic (troponin) values prior to PCI. All other PCI without evidence of myocardial necrosis coded as elective.
Partners PCP	Coded "yes" for patients with PCP in Partners EMR working primarily for Partners Healthcare system. Coded "no" for patients with PCP in Partners EMR not within Partners system or missing PCP data.
Insurance Type	Coded based on primary insurance listed in Partners EMR.
Site	Coded based on location of incident PCI procedure (either Massachusetts General Hospital [MGH] or Brigham and Womens Hospital [BWH])
Hypertension	Chart diagnosis of HTN prior to or at time of incident PCI
Hyperlipidemia	Chart diagnosis of HLD prior to or at time of incident PCI, LDL-C >129 at time of incident PCI or Triglycerides >150 at time of incident PCI
Type 2 Diabetes	Chart diagnosis of DM2 prior to or at time of incident PCI, or Hemoglobin A1c > 6.4 at time of incident PCI
Peripheral Arterial Disease	Chart diagnosis of PAD prior to or at time of incident PCI or history of peripheral arterial intervention
Smoking	Chart history of smoking (codified as current smoker, former smoker (quit >1 month prior to PCI), or never smoker). For analysis, variable was condensed into never smoker or ever smoker (either current or former).
Coronary Artery Disease	Chart diagnosis of CAD prior to or at time of incident PCI or history of CABG or prior PCI

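### The SAP's 90-day nonfatal MI definition does not require a new event, so read literally it counts the index MI in most patients treated for MI and pulls this exploratory comparison toward no difference

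*SAP*

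**What the plan says.** The D.7 row for 90-day nonfatal MI reads "Chart diagnosis of or admission for myocardial infarction (without subsequent death) within 90 calendar days of incident PCI as noted in Partners EHR". The stroke row directly above it is worded differently: "Chart diagnosis of or admission for new stroke within 90 calendar days of incident PCI as noted in Partners EHR". The two repeat-PCI rows also name a repeat procedure. The MI row has no such qualifier.

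MI is also an entry route. Protocol III (Sample size) plans "100 with myocardial infarction, 50 with symptomatic coronary artery disease without myocardial infarction". D.7 codes the reason for PCI from much the same source as the endpoint: "Myocardial infarction (MI) coded as chart diagnosis of MI or positive serologic (troponin) values prior to PCI". SAP D.2.b lists PCI type among the matching factors for controls.

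SAP Section J uses Cox models to "assess efficacy of the intervention on reducing rates of repeat PCI, stroke, non-fatal MI, cardiovascular cause of death and all cause death", counting 90 days from enrollment, whereas D.7 counts from the incident PCI. One SAP table shell also compares MACE, which is not defined. Section K treats everything except 90-day rehabilitation enrollment as exploratory.

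**The concern.** The endpoint overlaps with the entry criterion. A patient admitted with an acute MI and treated by PCI can have that same MI recorded at the procedure, on the discharge record and at a later visit. Each entry is a chart diagnosis of MI inside the 90-day window. Nothing in the definition separates it from a second infarction.

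Applied as written, the variable would mostly measure why patients entered the study. A recurrent MI in someone already counted for the index MI would add nothing. The Section J question on nonfatal MI could then be answered only from patients not already counted.

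**Working it through.** **Inputs from the documents.** Planned mix: 100 with MI and 50 without (Protocol III). Group sizes: 150 app users and 450 controls (SAP D.8). Matching on PCI type (SAP D.2.b), so the MI share should be about equal in the two groups.

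**Assumed input.** The documents give no 90-day rate of new MI. I take r = 1% to 10% in controls, equal in MI and non-MI patients, and suppose that the app halves it (true risk ratio 0.50).

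**Step 1: planned share with an index MI.** 100 + 50 = 150, the stated total. s = 100/150 = 66.7%. The same share of 450 controls is 300.

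**Step 2: recorded rates on the literal wording.** If every index MI counts, the control rate is s + (1 − s)r and the app rate is s + (1 − s)r/2. With s = 2/3:

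| Assumed r | Controls | App | Apparent risk ratio |
|---|---|---|---|
| 1% | 67.00% | 66.83% | 0.998 |
| 2% | 67.33% | 67.00% | 0.995 |
| 5% | 68.33% | 67.50% | 0.988 |
| 10% | 70.00% | 68.33% | 0.976 |

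Index MIs are s/[s + (1 − s)r] of counted control patients: 99.5% at r = 1% and 95.2% at r = 10%. With r equal in both strata, the share of true recurrences hidden behind an index MI is s, or two thirds.

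**Step 3: other values of s.** The achieved mix may differ, and some patients coded as MI may carry no MI diagnosis. If only 75 of the 100 did, s would be 75/150 = 50%. At r = 5%, a true ratio of 0.50 appears as 0.976 with s = 50% and 0.994 with s = 80%. Over r = 1% to 10%, s = 50% gives 0.995 to 0.955.

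**Step 4: power.** Two-proportion comparison, 150 against 450, two-sided alpha 0.05 (the SAP does not state sidedness), counting only results in favor of the app. At r = 5%, power is about 22% when only new events count (5.0% against 2.5%). It is about 4% on the literal wording (68.33% against 67.50%), where chance alone gives 2.5% in that direction.

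These are crude proportions, not Cox hazard ratios. The index events would enter the Cox model in about equal proportion in the two groups and pull its estimate the same way, but the exact figures would differ.

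**The case against.** The strongest reply is that the intent is plain. D.7 codes baseline conditions as present at or before the procedure, gives the index MI its own variable (PCI type), and uses the same within-so-many-days phrase for outcomes such as rehabilitation and death that can only come later. Section J counts from enrollment, which follows the PCI. An abstractor might well leave out the index event unprompted.

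This shows what was meant, but it does not repair the rule. Under the Protocol's main recruitment route (Subject Enrollment, Overview), patients are onboarded the day after PCI, before they go home. Diagnoses of the index MI entered at discharge or follow-up therefore fall after both the PCI and enrollment. A historical control has no enrollment date at all, so Section J's origin cannot be applied to both groups.

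Three stronger readings are tempting, and the documents do not support them:

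- *Every patient with an index MI is an event on day 0.* PCI type can be coded as MI on troponin alone, and such a patient may have no MI diagnosis or MI admission in the chart. Two thirds is also only the Protocol's planned mix; the SAP keeps the total of 150 without the split.
- *The definition would create a false app effect.* Matching on PCI type spreads index MIs about evenly, so the main effect is dilution. Different coding in 2015–2017 and 2018–2019 is possible, but nothing in the documents shows it.
- *The hospitalization rows count the index stay.* The 30-day row, "Admission date to a Partners hospital within 30 calendar days of incident PCI", does not exclude it. However, the Protocol outcomes, the SAP table shells and the SAP figure list all call the outcome readmission, which largely settles the meaning.

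**Conclusion.** The point stands for the nonfatal MI row: wrong as written, low consequence. On the literal reading, up to about two thirds of participants and matched controls meet the endpoint through the index MI. A true halving of new MI would then look like a risk ratio of about 0.98 to 1.00. That range rests on the planned 100/50 mix, every index MI being counted, and an assumed new-MI rate of 1% to 10%. If fewer index MIs are counted, the dilution is smaller but still severe.

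The consequence is low because the endpoint is exploratory and the rehabilitation analysis does not use it. Even with a correct definition, power at an assumed 5% rate is only about 22%. MACE has the same defect only if it includes this variable, which the SAP does not say.

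**What to change.** Reword the D.7 row along these lines, keeping its clause on death: *a new myocardial infarction, distinct from the index MI, diagnosed in the chart or causing admission after the incident PCI and within 90 days; diagnoses of the index MI carried forward in the record do not count*. Starting after the PCI, not after discharge, keeps in-hospital reinfarction in the endpoint.

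Define MACE and, if it includes MI, use the same rule. Use one time origin in D.7 and Section J that exists for both app users and controls. As a minor consistency point, word the hospitalization rows as readmission after the index stay, to match the table shells.

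The cost is one abstraction rule and a recheck of MI events already recorded. The SAP is dated 12/28/19, after the 09/2019 end of follow-up for the intervention arm, so some events may already have been abstracted.
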